7.1. Agent Administration (BMS-986156 dose escalation / de-escalation) and SBRT

Following enrollment, patients will be categorized into appropriate treatment groups.

Treatment group 1) Ipilimumab + BMS-986156 (30 or 100 mg) x 4 for safety assessment (No SBRT) → Nivolumab x 26.

Ipilimumab dose will be modified based on the outcome of DLT assessment, as described below.

Treatment group 2) Sequential (late SBRT) Ipilimumab + BMS-986156 x 2 → SBRT → Ipilimumab + BMS-986156 x 2 → Nivolumab x 26.

BMS-986156 dose as determined in group 1.

Ipilimumab dose will be modified based on the outcome of DLT assessment, as described below.

Treatment group 3) Concurrent (early SBRT) Nivolumab (480mg) + BMS-986156 (30 mg) + SBRT → Nivolumab + BMS-986156 x 3 → Nivolumab x 22.

BMS-986156 dose will be modified based on the outcome of DLT assessment, as described below.

In the event that patients meet criteria for multiple groups (i.e. exhibit treatable liver and lung metastasis), patient will be assigned to one group based on physician preference guided by

SBRT dosimetric considerations. Assignment may include evaluation of competing treatment plans with attention to normal tissue toxicities.

In the event that a treatment plan cannot reasonably meet dose constraints for 50 Gy in 4 fractions, then a separate plan will be generated for 60 Gy in 10 fractions. In the event that the subsequent treatment plan cannot reasonably meet dose constraints for 60 Gy in 10 fractions, then % PTV coverage can be reduced to make it safe.

All studies will be conducted with the following treatment scheme: Patients will be simulated up to 3 weeks prior to the anticipated SBRT start date. The first SBRT fraction will optimally be administered on a Monday. Patients receiving sequential SBRT will start SBRT about 1 week after the second dose of ipilimumab and BMS-986156. Patients receiving concurrent SBRT will start SBRT on day 1 of cycle 1 (with nivolumab and BMS-986156). If scheduling does not permit infusions and radiation to fall on the same day then SBRT of 50 Gy in 4 fractions may be administered starting day 2 of cycle 1.

Prior to starting each treatment cycle, patients will arrive at the Clinical Center for Targeted Therapy or Thoracic Medical Oncology Clinic and undergo safety assessments. In all groups, safety will be assessed by physical examination, observation and adverse experiences, and monitoring clinical chemistry and hematology. Disease progression will be based upon the irRC Criteria. All patients will be evaluated for toxicity upon their first receipt of the trial drug(s) and for therapy response after receiving at least 2 doses of drugs and at least half the scheduled radiation doses.

7.1.1 Dose escalation / de-escalation of BMS-986156 when combined with ipilimumab based on a (3+3) design to determine MTD

Ipilimumab (Yervoy™)

Ipilimumab (3 mg/kg) will be administered as a single 90 minute (+/- 15 minutes) intravenous infusion on the first day of each cycle, every 21 days (\pm 3d).

BMS-986156

BMS-986156 (30 mg or 100 mg) will be given as a single 60 min (+/- 15 minutes) intravenous infusion on the first day of each cycle (\pm 3d). When given in combination with Ipilimumab, BMS-986156 will be given every 21 days (\pm 3d).

7.1.1.1 Group 1: Dose Escalation of BMS-986156 when combined with ipilimumab

Treatment group 1: A modified 3+3 dose escalation then expansion to a total of 10 patients per arm (escalation + expansion, if applicable) will be performed on two dose levels of this combination therapy.

- The first 3 subjects will be enrolled at dose level 1 (3 mg/kg ipilimumab + 30 mg BMS-986156).
 - If 0 out of these 3 patients have a DLT, 3 patients will then be enrolled on dose level 2 (3 mg/kg ipilimumab + 100 mg BMS-986156).
 - If 1 of 3 subjects have a DLT in dose level 1 (30 mg), 3 more patients will then be enrolled at this dose level. If only 1 of the 6 total subjects at dose level 1 has a DLT, then 3 patients will then be enrolled on dose level 2, 100 mg BMS-986156.
 - Additionally, 4 patients will be enrolled on dose level 1 to a total of 10 patients at 30 mg BMS-986156.
 - If 2 of 3 subjects have a DLT at dose level 1, then dose escalation is stopped and the MTD is reached (dose level 1).
- Subjects will be receiving 3 mg/kg ipilimumab + 100 mg BMS-986156 at dose level 2.

- At this dose level, if 0 of the 3 subjects have a DLT, then both dose level 1 and dose level 2 will be expanded to more patients so that each arm has a total of 10 patients enrolled.
- If 1 of the 3 subjects at dose level 2 have a DLT, 3 more subjects will then be enrolled at this dose level. If only 1 of the 6 total subjects at dose level 2 have a DLT, both dose level 1 and dose level 2 will be expanded to more patients so that each arm has a total of 10 patients enrolled. If 2 of the 6 total subjects at dose level 2 have a DLT, then dose escalation is stopped and the MTD is reached (dose level 1). Only dose level 1 will be expanded to a total of 10 patients enrolled.
- If 2 of 3 subjects at dose level 2 have a DLT, then dose escalation is stopped and the MTD is reached (dose level 2).
- The expansion phase dose will be selected based on safety and response readouts. For example, the dose exhibiting the best therapeutic response or pharmacodynamic profile with the best safety profile.

Dose Escalation of BMS-986156 when combining with Ipilimumab.

Dose Level 1 3 mg/kg Ipilimumab + 30 mg BMS-986156

Dose Level 2 3 mg/kg Ipilimumab + 100 mg BMS-986156

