Day 1 and every 21 days: Ipilimumab therapy at 3 mg/kg as a 90 minute intravenous (IV) dose and BMS-986156 (dose as determined in group 1) as a 60 min IV will be given in an outpatient setting. Dose cycles will be repeated every 21 days: on days 1, 22, 43, and 64 for a total of 4 cycles. Nivolumab (480 mg Q4W) will start day 85 and continue every 28 days for 26 cycles. Enrollment of this group will start based on the following criteria. If 2 out of 6 patients, or less, display DLTs, then, enrollment of group 2 can begin. Alternatively, if 3 out of 6 patients, or more, display DLTs, then, enrollment of group 2 cannot begin until 10 patients have been treated in group 1.

SBRT: SBRT will be given after 2 doses of ipilimumab and BMS-986156 on days 29-32 for 50 Gy in 4 fractions or on days 29-40 for 60 Gy in 10 fractions (no SBRT during weekends): SBRT will be directed at 1-4 targetable liver or lung lesion(s). To minimize treatment breaks, patients may start radiation on a Monday.

Group 2

[figure not shown]

Diagram of Treatment Schedule for Ipilimumab + BMS-986156 x 2 → SBRT → Ipilimumab + BMS-986156 x 2 → Nivolumab x 26 (Treatment group 2).

Group 3, 20 patients: Nivolumab + BMS-986156 x 1 + SBRT → Nivolumab + BMS-986156 x 3 → Nivolumab x 22

First dose of Nivolumab + BMS-986156 and SBRT will be given concurrently (early) and followed by Nivolumab + BMS-986156 x 3; then, Nivolumab monotherapy for 22 cycles. Nivolumab will be administered for a total of 26 cycles, either as a combination or monotherapy, in this group. Enrollment of patients for this group will start around the same time as group 1. Choice of treatment group will be at the discretion of PI and treating physician.

Nivolumab therapy at 480 mg dose will be given on day 1 as a 30 minute IV dose and BMS-986156 at 30 mg dose will be given on day 1, 29, 57, 85 as a 60 min IV in an outpatient setting. Nivolumab monotherapy will start on day 113 and will continue for 22 cycles.

SBRT: SBRT will be given on days 1-4 (days 2-5 are acceptable if scheduling does not permit radiation to begin same day as infusions) for 50 Gy in 4 fractions or on days 1-12 for 60 Gy in 10 fractions (no SBRT during weekends). SBRT will be directed at 1-4 targetable liver or lung lesion(s). To minimize treatment breaks, patients may start radiation on a Monday.

Group 3

[figure not shown]

Diagram of Treatment Schedule for Nivolumab + BMS-986156 x 1 + SBRT → Nivolumab + BMS-986156 x 3 → Nivolumab x 22 (Treatment group 3)

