7.1.1.2 Group 2: Dose De-Escalation of BMS-986156 when combined with ipilimumab plus SBRT

BMS-986156 dose as determined in group 1, for combination treatment with ipilimumab, before adding SBRT to the treatment regimen.

Treatment group 2: A modified 3+3 dose de-escalation then expansion to a total of 20 patients will occur at the MTD.

The first 3 subjects will be enrolled at dose level 1 (3 mg/kg ipilimumab + BMS-986156).

- If 0 out of these 3 patients have a DLT, 3 additional patients will then be enrolled on this same dose level.
- If 1 of 3 subjects have a DLT, 3 more patients will then be enrolled at this dose level. If only 1 of the 6 total subjects at dose level has a DLT, then this dose level will be considered safe and all other patient in this arm will be treated at this dose level.
- If 2 of 6 subject have DLT at dose level 1, then the dose will be de-escalated as per table below.
- If 2 of 3 subjects have a DLT at dose level 1, then the dose will be de-escalated as per table below

Dose De-Escalation of Ipilimumab when combining with BMS-986156 plus SBRT.

If MTD from group 1 finds the 30mg BMS-986156 then:

Dose Level 1 3 mg/kg Ipilimumab + 30 mg BMS-986156

Dose Level -1 1 mg/kg Ipilimumab + 30 mg BMS-986156

If MTD from group 1 finds the 100mg BMS-986156 then:

Dose Level 1	3 mg/kg Ipilimumab + 100 mg BMS-986156
Dose Level -1	1 mg/kg Ipilimumab + 100 mg BMS-986156
Dose Level -2	1 mg/kg Ipilimumab + 30 mg BMS-986156

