 - If 1 of 3 subjects have a DLT in dose level, 3 more patients will then be enrolled at this dose level. If only 1 of the 6 total subjects at dose level has a DLT, then this dose level will be considered safe and all other patient in this arm will be treated at this dose level.
 - If 2 of 6 subject has DLT then the dose will be de-escalated as per table below.
 - If 2 of 3 subjects have a DLT at dose level 1, then the dose will be de-escalated as per table below

Dose De-Escalation of BMS-986156 when combining with Nivolumab plus SBRT.

Dose Level 1	480mg Nivolumab + 30 mg BMS-986156
---------------------	------------------------------------

Dose Level -1 480mg Nivolumab + 10 mg BMS-986156**7.1.2. Reinduction for all arms**

Reinduction will be allowed for patients in which the treating physician feels there was benefit from the trial treatment. It will consist of repeating the original treatment using the same schedule for each arm. Radiation may be given during reinduction, but is not required. Pending the treating radiation oncologist judgment, additional radiation therapy to a previously non-irradiated lesion can be administered during re-induction. Timing of radiation during reinduction will be at the discretion of treating Radiation Oncologist.

The target lesion for radiation will be chosen by the treating radiation oncologist. The target lesion must not have been previously irradiated. The target lesion does not have to be within the same organ that was initially treated during the initial treatment (e.g. patients who received initial lung lesion irradiation can have liver or a bone lesion irradiated during re-induction). Radiation dose and fraction will be either at the initial dose (50 Gy in 4 fractions or 60 Gy in 10 fractions) or at a lower palliation dose (30 Gy in 10 fractions) and may also be combined with low dose radiation ranging from 200cGy-1000cGy in multiple fractions, at the discretion of the treating radiation oncologist.

Other tumor sites may be treated for palliation concurrently or sequentially if needed at the discretion of the treating radiation oncologist.

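### Group 1 escalation rules (7.1.1.1): at 100 mg, 2 of 3 DLTs makes 100 mg the MTD while 2 of 6 makes it 30 mg; at 30 mg, 2 of 3 names 30 mg the MTD and 2 or more of 6 has no outcome

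*Combined protocol and SAP*

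**What the plan says.** Section 7.1.1.1 describes a modified 3+3 with two levels, 30 mg and 100 mg of BMS-986156, each with ipilimumab 3 mg/kg.

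- **30 mg.** With 0 of 3 DLTs, 100 mg opens. With 1 of 3, three more patients are added, and 1 of 6 opens 100 mg. If "2 of 3 subjects have a DLT at dose level 1, then dose escalation is stopped and the MTD is reached (dose level 1").
- **100 mg.** "If 2 of the 6 total subjects at dose level 2 have a DLT, then dose escalation is stopped and the MTD is reached"; the bracket that follows names dose level 1, and only that level is expanded to 10. The next bullet says that if "2 of 3 subjects at dose level 2 have a DLT, then dose escalation is stopped and the MTD is reached (dose level 2").
- **Closing bullet.** The expansion dose is chosen on safety and response findings.

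The other groups follow a different rule. For group 2 (7.1.1.2): "If 2 of 6 subject have DLT at dose level 1, then the dose will be de-escalated as per table below". For group 3 (7.1.1.3): "If 2 of 6 subject has DLT then the dose will be de-escalated as per table below". Both lists also de-escalate at 2 of 3.

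Other provisions touch on group 1:

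- **Section 1, group 2:** "If 2 out of 6 patients, or less, display DLTs, then, enrollment of group 2 can begin". With 3 or more of 6, "enrollment of group 2 cannot begin until 10 patients have been treated in group 1".
- **Section 7.1, group 1:** "Ipilimumab dose will be modified based on the outcome of DLT assessment, as described below". No reduced ipilimumab level for group 1 follows.
- **Section 10:** a summary goes to the IND Office after every 3 evaluable patients, and its approval is needed before a dose level changes.
- **Section 10.1:** more than 33% DLTs in the expansion stops that level and falls back to the one beneath it. The IRB and the investigator review all DLTs and agree on any reduction.

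**The concern.** The first primary objective (2.1) is the safe dose of BMS-986156 with ipilimumab 3 mg/kg, and section 3.3 says that no clinical safety data exist for this pair. The group 1 rules are the plan's written means of reaching that answer. If they reward greater toxicity with a higher dose, or give no answer when toxicity appears, they fail in the situation for which an escalation rule is written. The result also travels: 7.1.1.2 takes the group 1 dose, 30 or 100 mg, as the level at which group 2 begins with SBRT.

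**Working it through.** The plan states no operating characteristics for these rules, so there is no figure of its own to reproduce. The check is a reading of the decision table followed by exact binomial path probabilities.

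**Step 1. Outcomes as written**

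| DLTs | Group 1, 30 mg | Group 1, 100 mg | Groups 2 and 3 |
|---|---|---|---|
| 2 of 3 | MTD = 30 mg | MTD = 100 mg | de-escalate |
| 3 of 3 | none | none | not listed |
| 2 of 6 | none | MTD = 30 mg | de-escalate |
| 3 or more of 6 | none | none | not listed |

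**Step 2. Direction of the 100 mg rules.** The observed rates are 2/6 = 33% and 2/3 = 67%; the first rejects 100 mg and the second names it the MTD. This does not depend on any assumed rate. If three more patients were treated after 2 of 3, the best possible total would be 2 of 6, which already rejects 100 mg.

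**Step 3. How often the 30 mg cells are reached.** Let p be the true DLT rate at 30 mg and q = 1 − p. The documents give no rate for this combination, so p is assumed. The low value, 6%, is the DLT rate that section 3.3 reports for ipilimumab 3 mg/kg with SBRT, which is a different regimen.

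- Exactly 2 of 3: 3p²q
- 3 of 3: p³
- 1 of 3, then exactly 2 of 6: (3pq²)²
- 1 of 3, then 3 or more of 6: 3pq² × (3p²q + p³)

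At p = 0.10: 3 × 0.01 × 0.90 = 0.027; 0.10³ = 0.001; 0.243² = 0.059; 0.243 × 0.028 = 0.007.

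| True rate at 30 mg | 6% | 10% | 20% | 33% | 50% |
|---|---|---|---|---|---|
| Exactly 2 of 3 (30 mg named MTD) | 0.010 | 0.027 | 0.096 | 0.219 | 0.375 |
| 3 of 3 (no outcome) | 0.000 | 0.001 | 0.008 | 0.036 | 0.125 |
| Exactly 2 of 6 (no outcome) | 0.025 | 0.059 | 0.147 | 0.198 | 0.141 |
| 3 or more of 6 (no outcome) | 0.002 | 0.007 | 0.040 | 0.113 | 0.188 |
| 2 or more of 6 (sum of the last two) | 0.027 | 0.066 | 0.187 | 0.311 | 0.328 |
| Any result with 2 or more DLTs | 0.037 | 0.094 | 0.291 | 0.566 | 0.828 |

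**Step 4. How often 2 of 3 labels 100 mg the MTD.** With p = 0.10 at 30 mg, 100 mg opens with probability q³ + 3pq² × q³ = 0.729 + 0.243 × 0.729 = 0.906. With true rate p₂ at 100 mg, the overall chance is 0.906 × 3p₂²(1 − p₂):

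- p₂ = 20%: 0.906 × 0.096 = 0.087
- p₂ = 33%: 0.906 × 0.219 = 0.198
- p₂ = 50%: 0.906 × 0.375 = 0.340

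**The case against.** **The bracket may only mark where escalation stopped.** This fails on the text. In the 2-of-6 sentence the DLTs occur at level 2 and the bracket says level 1, so the bracket names the MTD.

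**Other safeguards would catch the error.** There are several: IND Office approval before dose levels change, the DLT review in 10.1, the closing bullet of 7.1.1.1, and the fact that no expansion at 100 mg is ordered after 2 of 3. Group 2 would also run its own 3+3, with two lower levels if it starts from 100 mg. These reduce the practical risk, and a reader should not infer that the whole process would carry a toxic dose forward unchecked. None of them changes the written rule, however. The section 1 criterion governs when group 2 opens, not the MTD. The 10.1 fallback has no level beneath 30 mg in group 1. Group 2 may be a weak backstop, because 7.2.1 opens its DLT definition by limiting MTD-defining events to toxicity of the irradiated organ.

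**The section's own 2-of-6 rule does not reach 30 mg.** This stands. A reader might infer that the 30 mg line breaks that rule, but the rule is written only for dose level 2. At 30 mg the conflict is with groups 2 and 3 and with ordinary 3+3 logic.

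**The problem may be rare.** This stands in part. The documents report no DLTs in 34 monotherapy patients and one in 225 with nivolumab. At an assumed 6%, exactly 2 of 3 at 30 mg occurs 1% of the time and 2 or more of 6 occurs 3%. But neither experience is with ipilimumab, and the rule exists for the less favourable case.

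**Rejecting 30 mg at exactly 2 of 6 is a choice.** This also stands. Section 1 allows group 2 to open at 2 of 6, and 10.1 stops only above 33%.

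**Conclusion.** The rules for 100 mg contradict each other, and the line for 2 of 3 is wrong whatever the true DLT rate. At 30 mg, naming that dose the MTD after 2 of 3 departs from the rule in groups 2 and 3. The outcomes for 2 or more of 6 at 30 mg, 3 of 3 at either level, and 3 or more of 6 at 100 mg are missing.

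The size depends on assumed rates. At 6/10/20/33/50% at 30 mg, exactly 2 of 3 occurs in 1/3/10/22/38% of trials, and 2 or more of 6 in 3/7/19/31/33%. With 10% at 30 mg, 100 mg is labelled the MTD through 2 of 3 in 9/20/34% of trials at true 100 mg rates of 20/33/50%. The defect is uncommon if both doses are well tolerated and likely to matter if they are not.

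The documents do not settle what exactly 2 of 6 at 30 mg should mean. That the plan must require rejection there is an inference they do not support, since they contain two thresholds.

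**What to change.** 1. **100 mg (7.1.1.1).** State that 2 or more of 3, or 2 or more of 6, means 100 mg exceeds the MTD. The MTD is then 30 mg if 30 mg is tolerated, and only 30 mg is expanded to 10.
2. **30 mg (7.1.1.1).** State that 2 or more of 3, or 3 or more of 6, means no tolerated dose is identified at ipilimumab 3 mg/kg, and that group 2 does not open at 3 mg/kg + 30 mg. Give the 33% stop in 10.1 the same outcome at 30 mg.
3. **Exactly 2 of 6 at 30 mg.** The sponsor should choose one outcome and make 7.1.1.1 and the group 2 opening rule in section 1 agree. The rule used at 100 mg and in groups 2 and 3 would reject the dose; the section 1 criterion would let group 2 open.

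A level of ipilimumab 1 mg/kg + 30 mg is an optional addition. It would need 3 to 6 patients (10 if expanded) and a change to the primary objective, which fixes ipilimumab at 3 mg/kg.

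**Cost.** Items 1 to 3 need a few sentences in 7.1.1.1, one in 10.1 and one in section 1, with no extra patients. The downside is that a tolerable 30 mg dose may be rejected. If exactly 2 of 6 also rejects, the chance is about 4% at a true 6% rate, 9% at 10% and 29% at 20%. If it does not, subtracting the exactly-2-of-6 row gives 0.037 − 0.025 = 0.012, 0.094 − 0.059 = 0.035 and 0.291 − 0.147 = 0.144. In either case group 2 would have no 3 mg/kg starting dose, so the plan should say what becomes of its 20 patients and of the group 2 comparisons in 10.2.1.

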Preliminary safety data on ipilimumab and SBRT: Combining ipilimumab and SBRT was safe with signs of efficacy (1, 25). In this phase I trial, treatments combining liver or lung SBRT at 50 Gy in 4 fractions or 60 Gy in 10 fractions concurrently or sequentially with ipilimumab at 3 mg/kg for 4 doses were considered safe. Two patients (6%) had DLTs, and even though rates of grade 3 treatment-related toxicity were 34% of treated patients, most were self-limiting and managed as an outpatient. Data on efficacy is encouraging, with 10% out-of-field irPR and 23% clinical benefit. Though these data are encouraging, the outcome may be improved by adding another I-O agent to the treatment regimen: we propose to test the safety and efficacy of combining BMS-986156 with ipilimumab + SBRT. However, there are no clinical data available on the safety of BMS-986156 + Ipilimumab. Treatment group 1 will be initiated to determine the safety of combining BMS-986156 (30 or 100 mg) and ipilimumab (3 mg/kg). After BMS-986156 dose determination in group 1, group 2 will be initiated with BMS-986156 (dose as determined in group 1) and ipilimumab plus SBRT. Recently, in our preclinical model of PD-1 resistance we have shown a dramatic improvement in radiation-induced abscopal responses with the addition of anti-GITR antibody. Moreover, an ongoing study (CA009-002) has recently provided human safety data following administration of a flat dose of nivolumab, another checkpoint inhibitor, in combination with BMS-986156, an anti-GITR monoclonal antibody (26). Altogether, these studies suggest that anti-GITR, a T-cell agonist, may potentiate a T cell mediated response and may contribute to abscopal responses observed when SBRT is administered with checkpoint inhibitors such as ipilimumab or nivolumab. These findings likewise prompted us to include additional arms involving concurrent SBRT administration with anti-GITR plus either ipilimumab or nivolumab in this study. Treatment group 3 will be initiated with nivolumab (480mg) plus BMS-986156 (30mg) and SBRT combination therapy.

Our hypotheses are as follows:

1) SBRT targeting a limited number of liver or lung metastasis in conjunction with ipilimumab and BMS-986156 or nivolumab and BMS-986156 combination therapy will result in improved local and systemic disease control.

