The Principal Investigator shall obtain all such permissions and authorizations as may be necessary or desirable to allow the collection and use of information protected under federal privacy laws and state privacy laws, including permission/authorization for monitoring and analysis (including re-analysis in combination with results of other studies), for regulatory submission purposes and for applicable reporting (if any).

Tumor response will be determined using the Immune Related Response Criteria (irRC) as described in section 8.3.

The Investigator is responsible for completing an efficacy/safety summary report, and submitting it to the IND Office Medical Affairs and Safety Group, for review and approval. This should be submitted after the first 3 evaluable patients in groups 1 and 3 complete 29 days of study treatment, and after the first 3 evaluable patients in group 2 complete 43 days of therapy initiation, and every 3 evaluable patients per group thereafter. IND Office approval must be obtained prior to advancing/changing dose levels.

A copy of the cohort summary should be placed in the Investigator's Regulatory Binder.

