10.1. Data Set Descriptions

For group 1, after BMS-986156, dose as determined in group 1, an additional 4 patient expansion per dose level (10 patients total for each dose level) will be enrolled in that group, at the determined dose from group 1, to help determine biological endpoints. Should DLTs occur in more than 33% of patients enrolled into this expanded group, dosing at that level will be stopped. The next lower dose level will be considered the safe dose. A review of all DLTs observed will be conducted, and the need to lower the dose will be based on the discussion and agreement between the IRB and the Investigator.

All patients who receive any ipilimumab, BMS-986156, or nivolumab will be considered evaluable for toxicity.

For toxicity and response: all patients receiving at least 1 (concurrent group) or 2 (sequential group) treatment with trial drugs and completed half of the planned radiation treatment (except for group 1 where no radiation is given) will be considered evaluable for toxicity and response and included in the efficacy data set.

Group 1: (Total of 20 patients: 10 patients with 30 mg and 10 patients with 100 mg of BMS-986156, when combined with ipilimumab at 3mg/kg). Nivolumab (480mg) Q4W monotherapy will be administer for 26 cycles.

Group 2: 20 patients: trial drugs, two doses of ipilimumab (3mg/kg) combined with BMS-986156 (dose as determined in group 1) are given before SBRT. SBRT is given sequentially; followed by 2 more doses of ipilimumab + BMS-986156. Nivolumab (480mg) Q4W monotherapy will be administer for 26 cycles.

Group 3: 20 patients: First dose of trial drugs nivolumab (480 mg) and BMS-986156 (30 mg) are given concurrently with SBRT; followed by 3 doses of nivolumab (480 mg) and BMS-986156 (30 mg). Finally, Nivolumab as monotherapy for 22 cycles. Nivolumab will be administered for a total of 26 cycles in this group.

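### Group 1 dose-finding rule is reversed at dose level 2: 2 of 6 DLTs makes 30 mg the MTD, but the worse result of 2 of 3 makes 100 mg the MTD

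*Combined protocol and SAP*

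**What the plan says.** Section 7.1.1.1 describes a modified 3+3 escalation with two levels. Level 1 is 3 mg/kg ipilimumab with 30 mg BMS-986156, and level 2 is the same ipilimumab dose with 100 mg.

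Two of the level 2 bullets matter here:

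- For 2 DLTs in 6, the text is "of the 6 total subjects at dose level 2 have a DLT, then dose escalation is stopped and the MTD is reached (dose level 1"), and only level 1 is then expanded to 10 patients.
- For 2 DLTs in 3, the text is "2 of 3 subjects at dose level 2 have a DLT, then dose escalation is stopped and the MTD is reached (dose level 2"). It does not say which level, if any, is expanded.

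At level 1, escalation after an initial single DLT requires that "only 1 of the 6 total subjects at dose level 1 has a DLT". The stopping bullet reads "If 2 of 3 subjects have a DLT at dose level 1, then dose escalation is stopped and the MTD is reached", and it names level 1 itself as that MTD.

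Section 7.1.1.2 carries the result into group 2. Under the line "If MTD from group 1 finds the 100mg BMS-986156 then", group 2 starts at 3 mg/kg ipilimumab plus 100 mg, with SBRT. Section 3.3 states that "there are no clinical data available on the safety of BMS-986156 + Ipilimumab".

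**The concern.** A dose-finding rule should never respond to more observed toxicity by keeping a higher dose. This one does: moving from 2/6 to 2/3 at level 2 raises the declared MTD from 30 mg to 100 mg.

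Finding the safe dose of BMS-986156 with ipilimumab is the first primary objective (section 2.1). Group 1 exists to answer it because the combination has no prior human safety data. If the faulty branch is reached and followed, group 2 patients start at a dose at which two of the first three patients had a DLT, and radiation is added. If group 2 then has to step down, its first step lowers ipilimumab and leaves BMS-986156 at 100 mg.

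The rule also has gaps. It gives no instruction for 3/3 at either level, for 2 or more of 6 at level 1, or for 3 or more of 6 at level 2.

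**Working it through.** **Step 1. The rules side by side.**

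| Where | Result | Observed rate | Stated consequence |
|---|---|---|---|
| Group 1, level 2 (7.1.1.1) | 2/6 | 33% | MTD is level 1 (30 mg) |
| Group 1, level 2 (7.1.1.1) | 2/3 | 67% | MTD is level 2 (100 mg) |
| Group 2 (7.1.1.2) | 2/3 or 2/6 | 67% or 33% | De-escalate |
| Group 3 (7.1.1.3) | 2/3 or 2/6 | 67% or 33% | De-escalate |
| Group 1 expansion (10.1) | above 33% | – | Stop; next lower level is the safe dose |

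Only the second row keeps the dose after excess toxicity. The bracketed level cannot mean the level at which the DLTs occurred, because the 2/6 bullet also concerns level 2 patients and names level 1.

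**Step 2. How often the faulty branch matters.** The plan states no operating characteristics, so there is no figure to reproduce. Let p be the true DLT rate at level 2 (assumed) and q = 1 − p. Outcomes are binomial in cohorts of three, and all results are conditional on level 2 being opened.

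- Corrected rule: 100 mg is kept after 0/3, or after 1/3 followed by 0/3. Probability = q³ + 3pq² × q³.
- As written: add the 2/3 branch. Addition = 3p²q.

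Example at p = 0.3: q³ = 0.343 and 3pq² = 0.441, so the corrected rule gives 0.343 + 0.441 × 0.343 = 0.494. The addition is 3 × 0.09 × 0.7 = 0.189, and the total is 0.683.

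| Assumed p | Corrected | Added by the 2/3 line | As written |
|---|---|---|---|
| 0.10 | 0.906 | 0.027 | 0.933 |
| 0.20 | 0.709 | 0.096 | 0.805 |
| 0.30 | 0.494 | 0.189 | 0.683 |
| 0.40 | 0.309 | 0.288 | 0.597 |
| 0.50 | 0.172 | 0.375 | 0.547 |
| 0.60 | 0.082 | 0.432 | 0.514 |

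**Step 3. The expansion stop.** Section 10.1 says "Should DLTs occur in more than 33% of patients enrolled into this expanded group, dosing at that level will be stopped". The 2/3 bullet orders no expansion, so this step assumes that level 2 is expanded to 10 after 2/3, which means 7 more patients. The section does not say which patients count, so there are three readings.

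- All 10 counted at the end: 3/10 is 30% and 4/10 is 40%, so 4 or more stops. After 2/3, 100 mg survives with at most 1 DLT in 7. Surviving part = 3p²q × P(X ≤ 1 | 7, p).
- Only the 7 added counted: 2/7 is 29% and 3/7 is 43%, so 3 or more stops. Surviving part = 3p²q × P(X ≤ 2 | 7, p).
- All patients at the level counted, and read at the first three-patient review: 2/3 already exceeds 33%, so nothing survives. On this reading section 10.1 contradicts the bullet directly.

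| Assumed p | All 10 | Only the 7 added | Read at 2/3 |
|---|---|---|---|
| 0.10 | 0.023 | 0.026 | 0 |
| 0.20 | 0.055 | 0.082 | 0 |
| 0.30 | 0.062 | 0.122 | 0 |
| 0.40 | 0.046 | 0.121 | 0 |
| 0.50 | 0.023 | 0.085 | 0 |
| 0.60 | 0.008 | 0.042 | 0 |

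In the first two readings the stop works only by treating more patients at 100 mg.

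**Step 4. Outcomes with no stated branch.**

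- Level 1: p³ + 3pq² × P(X ≥ 1 | 3, p) = 0.067, 0.195, 0.317 and 0.403 at p = 0.1, 0.2, 0.3 and 0.4.
- Level 2: p³ + 3pq² × P(X ≥ 2 | 3, p) = 0.008, 0.048, 0.122 and 0.216 at the same rates.

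**The case against.** The strongest reply is that this is a typing slip with a clear intent. The section is headed as a 3+3 design, groups 2 and 3 step down in the same situation, and one digit puts it right. That is probably how the error arose. It still stands in the operative rule that sets a dose, and a team following the text would name 100 mg.

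The second reply is that other safeguards would catch it. Section 10 requires a safety summary for review after the first three evaluable patients and every three thereafter, and adds that "IND Office approval must be obtained prior to advancing/changing dose levels". Section 10.1 calls for review of all DLTs, with any lowering of the dose agreed between the IRB and the investigator. Section 7.1.1.1 lets the expansion dose depend on safety and response, and group 2 has its own de-escalation. These make automatic carry-through less likely, and that part of the objection stands. None of them changes the stated MTD. The group 2 safeguard is also uncertain, because section 7.2.1 says that the DLTs defining the MTD with radiation are those of the irradiated organ and then gives a general list.

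The third reply is that high DLT rates are unlikely. Ipilimumab 3 mg/kg with SBRT had 6% DLTs (section 3.3). BMS-986156 alone had none in 34 patients (section 3.1.2), and with nivolumab it had one in 225, at 800 mg (section 3.1.4). At p = 0.06 the faulty line adds 3 × 0.0036 × 0.94 = 0.010. Level 2 must also open first: if both levels share one rate, the unconditional addition is 0.494 × 0.189 = 0.093 at 30% and 0.309 × 0.288 = 0.089 at 40%. These points are fair. The effect is small if the combination is well tolerated, but none of those studies tested this pair of drugs.

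Finally, the gaps are milder than the reversal. Most readers would take 2 of 3 to mean 2 or more, and 2 or more of 6 at level 1 plainly blocks escalation. What is missing there is the MTD label.

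**Conclusion.** The concern holds. At level 2 the rule in section 7.1.1.1 is not monotone in toxicity: the worse result keeps the higher dose, and the rest of the document points the other way without correcting it.

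The contradiction itself rests on the text and needs no assumption. Its size depends on the unknown DLT rate at 100 mg. Before the expansion stop it is negligible near 6 to 10% and substantial from about 30% upward, which is where a dose-finding rule most needs to protect patients. If level 2 is expanded after 2/3 and the stop is applied at the end, the surviving excess over the tabulated rates is at most about 0.06 (all 10 counted) or 0.12 (only the 7 added). It is zero if the stop is read at 2/3. Because group 2 inherits the dose and the combination is untested, this should be corrected before the rule is used.

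**What to change.** Amend section 7.1.1.1 as follows:

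- **Level 2:** 2 or more DLTs among the first 3 patients, or among 6, stops escalation. The MTD is dose level 1, and only dose level 1 is expanded.
- **Level 1:** 2 or more DLTs among the first 3 patients, or among 6, stops escalation, and this level is not declared tolerated.

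Writing 2 or more in each place also closes the unstated branches. In the same amendment it would help to say whether the six patients in the group 2 opening criterion (section 1) are counted per dose level or pooled, and whether the 33% stop in section 10.1 counts all 10 patients or only those added. The core correction does not depend on either clarification.

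The cost is a few lines of protocol wording, with no extra patients, visits or time.
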